## 8 QUALITY ASSURANCE & CONTROL

### 8.1 RISK ASSESSMENT

The Quality Assurance (QA) and Quality Control (QC) considerations will be reviewed throughout the study based on a formal Risk Assessment, which acknowledges the risks associated with the conduct of the trial and how to address them with QA and QC processes. The risk assessment will be used to develop and amend the trial Quality Management Plan.

There are risks already identified which have been addressed within the protocol and trial procedures. Participants may believe themselves completely protected by Truvada and take risks they would not otherwise have done. Determining the extent of this is an important outcome measure in the pilot. Investigators and other members of the clinic study team will help participants to consider Truvada as one component of their overall risk reduction strategy, they will emphasise the limitations of Truvada and the importance of adherence. Participants will need to provide sensitive information on a regular basis, however the questions do not differ substantially from those routinely asked in GUM clinics and all information will be held in compliance with the Data Protection Act, and linked using only their trial number at MRC CTU, and GUM clinic numbers at PHE. Date of birth and soundex will be used to cross check the new HIV diagnoses database at PHE.

Although there is a risk of mild to moderate side effects when taking Truvada the more serious side effects of renal tubular dysfunction and lactic acidosis have not been reported in HIV negative populations. There is a small risk of resistance arising from continued treatment with Truvada following seroconversion.

### 8.2 CENTRAL MONITORING AT MRC CTU

MRC CTU staff will review the reports generated from the database that list inconsistencies and missing data with regard to

- Eligibility criteria
- Follow-up schedule
- Trial specific procedures including collection of outcome data

Other essential trial issues, events and outputs will be detailed in the Monitoring and Quality Management Plan that is based on the trial-specific Risk Assessment.

### 8.3 ON-SITE MONITORING

The frequency, type and intensity of routine monitoring and the requirements for triggered monitoring will be detailed in the Monitoring and Quality Management Plan.

#### 8.3.1 DIRECT ACCESS TO PARTICIPANT RECORDS

Participating investigators should agree to allow trial-related monitoring, including audits, ethics committee review and regulatory inspections by providing direct access to source data and documents as required. Participants' consent for this must be obtained.

#### 8.3.2 CONFIDENTIALITY

We plan to follow the principles of the UK Data Protection Act.

## 9 STATISTICAL CONSIDERATIONS

### 9.1 METHOD OF RANDOMISATION

Randomisation will be performed centrally at the MRC CTU using a computer algorithm based on random permuted blocks stratified by site.

### 9.2 OUTCOME MEASURES

#### 9.2.1 MAIN OUTCOME MEASURES

Time to accrual of 500 participants

Retention at 12 and 24 months from randomisation

#### 9.2.2 OTHER OUTCOME MEASURES

- HIV infections acquired between trial entry and 12 months, and between 12 and 24 months
- Safety
  - Serious Adverse Reactions attributable to Truvada
  - Any adverse event leading to interruption or discontinuation of Truvada
  - Renal function estimated using serum creatinine at 12 months
  - Presence of viral resistance mutations likely to have been selected by Truvada (K65R, M184V) in participants who acquire HIV infection.
- Adherence:
  - Proportion of doses taken estimated from self-report
  - Proportion of days covered according to dispensing records for the daily schedule
  - Presence of drug as expected in a subset of selected participants
- Risk Compensation:
  - Number of sexual partners with whom had UAI, UIAI and URAI (unprotected defined as without a condom) between trial entry and month 12 and month 12 to month 24
  - Number of acts of AI, protected and unprotected by a condom, between trial entry and month 12 and month 12 to 24
  - Proportion of acts of AI protected by either condom, PrEP or both between trial entry and month 12 and month 12 to 24
  - Sexually transmitted infection (STIs) acquired between trial entry and month 12
  - Sexually transmitted infection (STIs) acquired between month 12 and month 24
- Other:
  - Facilitators and barriers to adherence to a personal risk reduction plan in a subset of selected participants

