## SUMMARY OF TRIAL

SUMMARY INFORMATION TYPE	SUMMARY DETAILS
ACRONYM	PROUD
Long Title of Trial	Pre-exposure Option for reducing HIV in the UK: an open-label randomisation to immediate or deferred daily Truvada for HIV negative gay men.
Version	1.3
Date	14 October 2014
ISRCTN #	ISRCTN94465371
NCT#	NCT02065986
EudraCT #	2012-002373-56
Study Design	A multi-centre, open label randomised design to immediate or deferred inclusion of pre-exposure prophylaxis as part of the package of HIV risk reduction interventions.
Type of Participants to be Studied	HIV negative men who have unprotected anal intercourse (UAI) with men
Setting	Genito-urinary medicine (GUM) clinics in the UK
Interventions to be Compared	All participants will be offered a risk reduction package that includes regular HIV testing, diagnosis and treatment of sexually transmitted infections (STI), support to reduce and eliminate high risk behaviour including free condoms, and other biomedical interventions such as post-exposure prophylaxis where relevant. With or Without the inclusion of daily oral Truvada.
Study Question	In order to determine whether the immediate inclusion of anti-retroviral pre-exposure prophylaxis (PrEP) as part of the HIV risk reduction package for men who have sex with men who are at risk of acquiring HIV is clinically effective and cost-effective, a large trial would need to be conducted.  The purpose of the pilot is to determine the feasibility of conducting such a trial in the UK.
Main Outcome Measures	Time to accrual of 500 participants Retention at month 12 and 24
Other Outcome Measures	HIV infection between randomisation and month 12 .  Safety: 
 
• Serious Adverse Reactions attributable to Truvada
 
• Adverse events that lead to interruption or cessation of Truvada
 
• Renal function estimated using serum creatinine at 12m
 
• Frequency of viral resistance in men who acquire HIV
 

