### 7.3.1 INVESTIGATOR ASSESSMENT

#### 7.3.1.A Seriousness

The investigator should determine at each visit, or telephone contact where this substitutes for a visit, whether or not a Serious Adverse Event has occurred since the previous record, using the definition given in [Table 7.1: Definitions](#).

If the event is serious, then an SAE Form must be completed and the MRC CTU notified within 24 hours.

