#### 7.3.1.C Causality

The investigator must assess the causality of all serious events or reactions in relation to the trial therapy using the definitions in [Table 7.2: Assigning Type of SAE Through Causality](#). There are five categories: unrelated, unlikely, possible, probable, and definitely related. If the causality assessment is unrelated or unlikely to be related, the event is classified as an SAE. If the causality is assessed as possible, probable or definitely related, then the event is classified as an SAR.

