#### 7.3.1.E Notification

The MRC CTU should be notified of all SAEs within 24 hours of the investigator becoming aware of the event.

Investigators should notify the MRC CTU of all SAEs occurring from the time of randomisation until 30 days after the last protocol treatment administration. SARs and SUSARs must be notified to the MRC CTU until trial closure. Any subsequent events that may be attributed to treatment should be reported to the MHRA using the yellow card system.

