## **7.4 MRC CTU RESPONSIBILITIES**

Medically-qualified staff at the MRC CTU and/or a medically-qualified delegate will review all SAE reports received. The causality assessment given by the local investigator at the hospital cannot be overruled; in the case of disagreement, both opinions will be provided in any subsequent reports.

The MRC CTU is undertaking the duties of trial sponsor and is responsible for the reporting of SUSARs and other SARs to the MHRA, research ethics committees and Gilead Sciences, Inc as appropriate. Fatal and life-threatening SUSARs must be reported to the MHRA within 7 days of the MRC CTU becoming aware of the event; other SUSARs must be reported within 15 days.

The MRC CTU will also keep all investigators informed of any safety issues that arise during the course of the trial.

The MRC CTU, as Sponsor, will submit Development Safety Update Reports (DSURs) to the MHRA, Ethics Committees and Gilead Sciences, Inc.

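### The only serious-event outcome depends on open-label attribution to Truvada and gives no between-group comparison, and the rules for ascertaining SAEs conflict, so an all-SAE comparison could be biased in either direction

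*Protocol*

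**What the plan says.** Section 9.2.2 lists "Serious Adverse Reactions attributable to Truvada" as the serious-event outcome, and the Summary of Trial does the same. The design is "A multi-centre, open label randomised design to immediate or deferred inclusion". Section 7.3.1.C leaves causality to the investigator: "If the causality is assessed as possible, probable or definitely related, then the event is classified as an SAR". Section 7.4 adds: "The causality assessment given by the local investigator at the hospital cannot be overruled". If the central reviewer disagrees, both opinions are reported.

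Under Section 5.2, deferred men have no access to Truvada before month 12, or earlier if the Trial Steering Committee recommends it.

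On collection, Section 7.3.1.A has the investigator determine at each visit "whether or not a Serious Adverse Event has occurred since the previous record". Section 7.3.1.E says: "Investigators should notify the MRC CTU of all SAEs occurring from the time of randomisation until 30 days after the last protocol treatment administration". It continues: "SARs and SUSARs must be notified to the MRC CTU until trial closure". Section 5.2.4 asks that men who stop Truvada be kept in the study.

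**The concern.** The trial randomises men to a group that is off drug for up to a year, which is the setting in which an excess of serious events can be measured without anyone judging cause. The listed outcome does not use it. A serious event counts only if an unblinded investigator already thinks Truvada may have caused it, and in untreated deferred men the count is zero by definition. A fracture admission rated unlikely to be related would not enter the serious-event outcome, although Section 7.1.2 names fractures and renal events as important to the safety evaluation. Section 11.2.1 also relies on the data monitoring committee being able to act on early evidence of harm.

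A later analysis by allocated group would depend on SAEs having been collected in the same way in both groups. The protocol does not secure that, and a statistical analysis plan cannot recover events that were never asked about or never notified.

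**Working it through.** **Which listed safety outcomes allow a between-group comparison in the first 12 months?**

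- Attributed SARs: no. They require exposure to Truvada.
- Adverse events leading to interruption or discontinuation of Truvada: no. They also require exposure.
- Resistance mutations: only among men who acquire HIV, so not a general measure of harm.
- Creatinine at 12 months: yes. Section 6.2.4 requires annual visits, with serum creatinine, for all participants.

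**What does each section say about SAE ascertainment?**

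| Place | Rule | Effect |
|---|---|---|
| Assessment schedule | SAE assessment at quarterly, annual and exit visits, plus the first-month-on-PrEP contact | No on-drug limit, but the extra contact occurs only after starting drug |
| 6.4 | Asks one month after starting Truvada and quarterly | No on-drug limit on the quarterly question |
| 7.3.1.A | At each visit or substituting telephone contact | No on-drug limit |
| 6.2.3 | The quarterly SAE enquiry is written for periods on Truvada; 6.2.4 runs annual visits the same way | Untreated deferred men not covered |
| Table 7.1 | An adverse event needs a medicinal product to have been administered | Read literally, excludes untreated deferred men |
| 7.3.1.E | All SAEs from randomisation to 30 days after last administration | Cuts off men who stop; no end stated for a man never dosed |

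These rules cannot all govern. If 7.3.1.E governs, only men who have taken drug can reach the cut-off, and after it only events already rated as related are notified. If 6.2.3 and Table 7.1 govern, untreated deferred men contribute little or no ascertained SAE time, which would be a larger bias in the opposite direction.

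**How large might the 30-day cut be?** The protocol gives no stopping rate and no SAE rate, so there is no figure to reproduce. The inputs below are assumptions.

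Let a fraction q of the immediate group stop permanently at times t spread evenly over 0 to 12 months. Thirty days is 30/30.4375 = 0.986 months, so a man who stops at t loses 12 − 0.986 − t = 11.014 − t months, if positive. The mean loss per stopper is 11.014² / (2 × 12) = 5.05 months. The share of the group's first-year time lost is q × 5.05/12. If all stopped at month 1, it would be q × (12 − 1 − 0.986)/12 = 0.8345q.

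| q (assumed) | Even stopping times | All stop at month 1 |
|---|---|---|
| 5% | 2.1% | 4.2% |
| 10% | 4.2% | 8.3% |
| 20% | 8.4% | 16.7% |
| 30% | 12.6% | 25.0% |

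With a constant SAE rate and no true effect, the immediate-to-deferred ratio of SAE counts would be about 0.98 to 0.87 in the middle column and 0.96 to 0.75 in the last.

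**Would an all-SAE comparison be informative?** Section 1.4 gives 545 enrolled, about 272 per group. The 95% half-width of a risk difference is 1.96 × √(2p(1 − p)/272), which is 2.9, 3.7 or 5.0 percentage points for an assumed 12-month risk p of 3%, 5% or 10%. At the planned 250 per group (two-sided 5% level), power to detect a doubling is 26%, 57% or 88% from a deferred-group risk of 2%, 5% or 10%.

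**The case against.** The strongest reply is that Section 9.5 leaves analysis to a separate statistical analysis plan, where an SAE table by group is routine, and that this is a feasibility pilot. The first part stands to this extent: a reader might infer that the all-SAE comparison goes unused, but the protocol shows only that it is not a listed outcome. The reply does not reach the collection rules, which are fixed in the protocol. The second part limits the severity. At low event rates the comparison is imprecise and would detect only a large excess.

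Other stronger readings are tempting but not supported:

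- That the 30-day cut damages the listed outcome. It does not, because SARs and SUSARs are notified until trial closure. A late event after stopping still counts if rated at least possibly related. The cut affects only SAEs rated unrelated or unlikely.
- That the record is cut short only in men who took the drug, so the immediate group is undercounted. This follows 7.3.1.E alone. Section 6.2.3 and Table 7.1 point the other way, and 7.3.1.A still asks at every visit.
- That an all-SAE comparison would be the only one free of attribution. Twelve-month creatinine is another.
- That men stop mainly because they are ill. No section says so. Section 5.2.4 also allows stopping for changed behaviour or by free choice. Section 1.2.1 reports that 7 of 4,500 participants in earlier trials had to stop for toxicity. That is 0.16%, and at that rate the loss would be 0.0016 × 5.05/12, or about 0.07%. Stopping for any reason may be much commoner, but the protocol gives no figure.
- That the central reviewer's view is lost. It does not overrule the investigator's rating, but it is reported beside it.

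**Conclusion.** The point holds in two parts, both from the text alone. First, the only serious-event outcome rests on open-label attribution and cannot compare the randomised groups before deferred men start Truvada. Second, the sections on SAE ascertainment conflict, and none sets one window for both groups.

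Neither the direction nor the size of bias in an all-SAE comparison can be fixed from the protocol. The illustrative loss of about 2% to 13% of the immediate group's first-year SAE time assumes that 5% to 30% stop permanently at evenly spread times and that 7.3.1.E governs. Under Section 6.2.3 and Table 7.1 the shortfall would fall on untreated deferred men instead, and could be larger.

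Severity is minor to moderate: the pilot's main outcomes are unaffected, 12-month creatinine gives one unattributed comparison, and the remedy is cheap.

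**What to change.** In Section 9.2.2, add all SAEs regardless of attribution, by allocated group, from randomisation to month 12. Because deferred men were offered Truvada early after the recommendation of 9 October 2014, state a cut-off rule that applies identically to both groups, for example a common calendar date. Report the outcome with and without SAEs that qualify only through permanent discontinuation of Truvada (Table 7.1 footnote and Section 6.4), since untreated men cannot have those. Keep attributed SARs as a further outcome.

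Reconcile the assessment schedule, Sections 6.2.3, 6.4, 7.3.1.A and 7.3.1.E, and the adverse event definition in Table 7.1, so that SAEs are ascertained and notified over one window counted from randomisation, the same in both groups and not dependent on drug exposure. This concerns data collection only and changes no treatment rule.

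The cost is one outcome line, aligned wording in the sections named, one table, and a few more SAE forms for men who are off drug. The schedule already provides for SAE assessment at the quarterly, annual and exit visits.

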### 9.3 SAMPLE SIZE

The target of 500 participants (250 per treatment arm) for the pilot is a pragmatic choice, to guide whether 5000 participants can be enrolled over 2 years, as this is the anticipated target for an

adequately powered effectiveness trial in this population. It is also informed by the number of participants clinics have agreed to recruit to the pilot.

#### **9.4 INTERIM MONITORING & ANALYSES**

The Trial Steering Committee (TSC) for the PROUD Pilot study agreed that it was appropriate for key study outcomes to be monitored by an independent individual expert rather than a formally constituted IDMC when they reviewed the First TSC report. However, they recommended that a full Independent Data Monitoring Committee (IDMC) be constituted to review HIV infections by allocation following review of the Third TSC report in April 2014. .

An IDMC Charter will be drawn up that describes the membership of the IDMC, relationships with other committees, terms of reference, decision-making processes, and the timing and frequency of interim analyses (with a description of stopping rules and/or guidelines, if any).

#### **9.5 ANALYSIS PLAN**

The analyses will be described in detail in a full Statistical Analysis Plan. The primary aim of the pilot is to demonstrate the feasibility of an adequately powered trial. The rate of recruitment will be assessed by individual centre. Participant retention at 12 months, in particular in the deferred arm, will be compared with the assumption used in the sample size calculation for the full trial. Secondary analyses will compare sexual behaviour between the two groups as allocated, censoring patients at either HIV infection or, for participants with incomplete follow-up, at their last negative HIV test.

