### 1.4 PILOT EXPERIENCE AND TRIAL STEERING COMMITTEE RECOMMENDATIONS

The Pilot was slow to recruit in the first instance due to lack of PrEP awareness and limited clinic resources. From July 2013, accrual improved and enrolment closed on 30 April 2014 with 545 participants. Trial Steering Committee (TSC) has convened on six occasions, once prior to the initiation of the Pilot, four times to review progress and most recently to review a recommendation from the Independent Data Monitoring Committee (IDMC). At the outset of the trial, the data were monitored by an Independent Data Monitor who was a biostatistician, but in April 2014 the TSC recommended that a full IDMC be appointed, including a clinician and community representative with expertise and knowledge of the HIV epidemic in the UK. This decision was based on the possibility that the pilot sample may have sufficient power to answer the question of effectiveness, as the baseline characteristics suggested that the HIV incidence in the deferred group was going to be high compared to the overall population of gay men attending sexual health clinics. At this meeting they also recommended that the study team secure drug and support so that all participants could continue on PrEP through to the end of the pilot.

The IDMC has met on three occasions since June, and reviewed the accumulating data each month. As PROUD had no pre-determined protocol defined discontinuation rules, the IDMC agreed at its first meeting that a lower 95% confidence limit for the rate difference that exceeded 2.0 would be powerful evidence of an important effect of PrEP, and could be regarded as a useful guideline for recommending discontinuation of the trial in its present form. In the results examined in the third and most recent meeting, on 6th October 2014 this limit was exceeded. There appeared to be no trend over the initial year of follow-up time for the HIV infection rates in the two arms to be converging, and little prospect of new events in the immediate PrEP arm to be frequent enough over the rest of the proposed study period for the result to substantially change with continued follow up. On the basis of this, the IDMC recommended that the deferred arm could no longer continue, primarily on the basis of safety, due to a significant and potentially preventable risk of HIV infection in the deferred group compared to the immediate group.

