### 5.2.4 TREATMENT DISCONTINUATION

Treatment may be stopped early for any of the following reasons:

- HIV infection
- Unacceptable toxicity or adverse event
- Any change in the participant's sexual behaviour or circumstances that justifies the discontinuation of treatment in the clinician's opinion
- On the recommendation of the Trial Steering Committee/termination of the study by the Sponsor

The participant is free to interrupt or discontinue Truvada. They will be discouraged from doing so if they are continuing to have unprotected anal intercourse.

Even if participants are no longer taking Truvada, every attempt should be made to maintain them in the study. Participants who have confirmed HIV infection do not need further HIV tests but should continue, provided they are willing, to complete the sexual behavioural data and have the STI screens. If a participant is withdrawn from follow-up, refer to [Section 6.6 - Early Stopping of Follow-up](#).

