### 6.5.4 IN THE EVENT OF SEROCONVERSION

In the event of a seroconversion, information about all sex acts since the previous negative result, number of new partners, characteristics of partners, and adherence to condoms will be collected as is routine practice. Information regarding adherence to Truvada will also be elicited, if applicable. A sample for analysis of drug levels may be collected.

Participants can continue, should they wish to, to complete the short and long questionnaires and have the STI screens, although these can be collected at their routine HIV clinic visits if more convenient.

In accordance with national guidelines for newly diagnosed individuals, a genotypic drug resistance test should be performed to identify mutations which may have been transmitted from the infecting partner or acquired as a result of exposure to Truvada. This test should be performed on the earliest possible sample after seroconversion and a copy of the result sent to MRC CTU for data entry.

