### **At the request of the Trial Steering Committee:**

The protocol has been amended to accommodate and implement the Trial Steering Committee recommendations of 9th October 2014, namely that daily oral Truvada be offered to all participants in the PROUD pilot study as soon as possible and continued through to the end of the study. The protocol has also been updated to reflect the constitution of the IDMC.

A new section has been added to the introduction explaining the rationale for the change (Section 1.4). Sections 1.2.4, 5.2, 5.4, 6.6, 7.1.3 have been changed to reflect the earlier offer of PrEP to those in the deferred group from October 2014 onwards and the continued provision of PrEP beyond month 24 while the study is ongoing. Section 9.4 and 14.3 update the independent study monitoring arrangements

At the request of investigators and participants:

Section 5.2.3 has been amended to allow for dose modification when participants who have impaired renal function due to other causes wish and need to continue on Truvada. The modifications allowed are in line with the SMPC that supports the use of Truvada as treatment.

Section 6 has been modified to allow participants to provide the necessary information for safety and behaviour monitoring outside the study clinic times as it has proved easier for participants to attend evening and weekend clinics to have their routine HIV and STI screening and the results are readily available to study staff who can check these before prescribing.

The diaries and questionnaires have proved unpopular with participants and completion has been very low. The online participant database will continue to be available but we will ask participants to complete the monthly questionnaires in clinic during study visits or when they collect drug (Section 6.2.2 and 6.2.3).

Although the lack of daily and monthly behaviour data is disappointing, the annual data are available for analysis and the rate of STIs has been higher than anticipated and these provide an objective marker of risk behaviour. National guidelines have changed since the protocol was implemented and quarterly screens are recommended for MSM having condomless anal intercourse with partners of unknown or HIV negative status. Therefore the schedule has changed to reflect quarterly screens and the inclusion of hepatitis C, regardless of risk, at exit (Section 6.2.3, 6.2.4 is no longer needed, 6.2.5).

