Participants that have seroconverted have found it easier not to continue to attend the study visits, and Section 6.5.4 has changed accordingly.

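### Section 9.5 ends the sexual-behaviour comparison at HIV infection or the last negative HIV test, which discards usable behaviour reports and censors the arms unequally; any bias is probably modest.

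*Protocol*

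**What the plan says.** Section 9.5 states: "Secondary analyses will compare sexual behaviour between the two groups as allocated", and attaches to that comparison the rule "censoring patients at either HIV infection or, for participants with incomplete follow-up, at their last negative HIV test". The rule therefore governs behaviour as written.

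Section 9.2.2 lists the risk-compensation outcomes (partners, acts, share of acts protected, STIs). It sets the window for partner counts as "between trial entry and month 12 and month 12 to month 24", with matching windows for the others.

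Two sections provide for data after infection. Section 5.2.4 says that men with confirmed infection "should continue, provided they are willing, to complete the sexual behavioural data and have the STI screens". Section 6.5.4 is more permissive: "Participants can continue, should they wish to, to complete the short and long questionnaires and have the STI screens".

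Section 1.4 gives the imbalance in infection. The data monitoring committee acted on "a significant and potentially preventable risk of HIV infection in the deferred group compared to the immediate group".

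**The concern.** Both limbs tie the behaviour data to HIV testing, but the behaviour outcomes do not need an HIV test.

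- **Last negative test.** Where follow-up is incomplete, anything reported after the last negative test is lost, although it is as informative about behaviour as anything reported before it.
- **Infection.** Infection occurs after randomisation, depends on behaviour and is affected by allocation. Ending follow-up there censors more deferred than immediate men, so the later part of an as-allocated comparison no longer compares the groups as randomised.

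What is at stake is the risk-compensation result. Section 1.3 gives risk compensation as the reason for the open-label design, Section 11.2.1 rests equipoise on it, and Section 8.1 calls its extent an important outcome measure. The main outcomes of the pilot, accrual and retention, are not touched.

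**Working it through.** The protocol gives no figure for this point, so there is none to reproduce.

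**1. Can behaviour reports post-date the last HIV test?** Yes. The assessment schedule allows short questionnaires monthly between visits and at the first month on PrEP, with no HIV test at either. Section 6.5.1 allows monthly online completion. Section 6.2.3 allows the questionnaire to be completed at drug collection, and lets quarterly visits reuse tests taken since the previous visit. Direction by arm is undetermined. Section 1.4 asks for special efforts to reach immediate-group men who missed their last visit, so last-test dates may differ by arm, but nothing shows which way that moves the result.

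**2. What does the infection limb drop?** Only reports after infection. Diary and questionnaire completion was very low, however, and the Version 1.3 entry in Section 16 relies on what remains: "the annual data are available for analysis and the rate of STIs has been higher than anticipated". The long questionnaire covers 90 days (Section 6.5.1). A man infected before month 12 keeps his earlier reports but loses his month-12 one.

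**3. How large could the effect be?** Inputs:

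- 250 per arm (Section 9.3).
- 44% to 73% lower incidence on PrEP (Section 1.2.1, earlier trials).
- Deferred incidence 3 to 9 per 100 person-years, central value 5 (assumption).
- R, the seroconverters' mean in the dropped reports relative to the overall mean, 0.5 to 3 (assumption).
- No true risk compensation, so both arms have overall mean 1.

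Formulas, with λ the annual rate:

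- Share infected by month 12: f = 1 − exp(−λ).
- Share of 0–12 month person-time lost: p = 1 − (1 − exp(−λ))/λ.
- Mean left after censoring: (1 − fR)/(1 − f), or the same with p for person-time.
- Spurious ratio: immediate mean divided by deferred mean.

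At 5 per 100 person-years, f is 0.0488 in the deferred arm (12.2 men of 250). In the immediate arm it is 0.0276 at a 44% reduction (6.9 men) and 0.0134 at 73% (3.4 men). For R = 2 and 73%: immediate (1 − 0.0268)/(1 − 0.0134) = 0.986; deferred (1 − 0.0976)/(1 − 0.0488) = 0.949; ratio 1.040.

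| R | Month-12 ratio (44%; 73%) | Person-time ratio (44%; 73%) |
|---|---|---|
| 0.5 | 0.989; 0.982 | 0.994; 0.991 |
| 1 | 1.000; 1.000 | 1.000; 1.000 |
| 1.5 | 1.012; 1.019 | 1.006; 1.009 |
| 2 | 1.024; 1.040 | 1.011; 1.019 |
| 3 | 1.051; 1.084 | 1.023; 1.039 |

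Over incidences of 3 to 9 with R from 1.5 to 3, the month-12 ratio runs from 1.01 to 1.17 and the person-time ratio from 1.00 to 1.07. With R = 0.5 the month-12 ratio is 0.97 to 0.99.

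The committee's guideline in Section 1.4, a lower limit above 2.0 for the rate difference, has no stated unit. If it is per 100 person-years, a difference of 2.0 means 250 × 0.02 = 5 more deferred men infected per 250 in a year.

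**4. Against sampling error.** The 95% factor for a ratio of means is exp(1.96 × CV × √(2/250)). With an assumed coefficient of variation (CV) of 1 to 2 this is 1.19 to 1.42, above every ratio computed. For a binary outcome, assume 40% overall and 60% to 80% in seroconverters. The shift is then 0.5 to 2.8 percentage points, against a half-width of 1.96 × √(2 × 0.4 × 0.6/250) = 8.6 points.

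Unlike sampling error, the bias does not shrink with numbers. Section 1.3 calls the pilot's design identical to that of a main trial of about 5000. With 2500 per arm the same factor is 1.06 to 1.12, comparable with the bias at R = 2 to 3.

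**The case against.** The strongest defence is that behaviour while HIV negative is a coherent target. Section 1.2.3 describes risk compensation as a response to believing that PrEP protects against infection, which concerns men still at risk. Seroconverters stop Truvada (Section 5.6.4), and the share of acts protected by condom or PrEP means little for them. Including their later behaviour in the main analysis would add reports from diagnosed men off drug, mostly from one arm, which is a distortion of its own. This stands, and it makes the infection limb a choice to declare rather than a mistake. It does not justify the last-negative-test limb.

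It is also fair that collecting data does not oblige the trial to use them in every comparison, that Section 6.5.4 only permits continuation, and that little may exist: "Participants that have seroconverted have found it easier not to continue to attend the study visits". Annual questionnaires coincide with a required HIV sample (Section 6.2.4), which limits what the last-negative-test limb discards. These points reduce the size of the problem without removing it.

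A reader might infer something stronger: that the rule removes the highest-risk men, mainly from the deferred arm, and so manufactures apparent risk compensation. If a share p of deferred men with k times the partners of the others were deleted outright, and none from the immediate arm, the ratio would be 1 − p + kp: 1.03 at p = 0.03, k = 2, and 1.18 at p = 0.09, k = 3. The protocol does not support that reading. Censoring acts at infection, so earlier reports stay; immediate-arm infections are censored too; and nothing says how seroconverters behave after diagnosis. A reader might also infer that the rule was meant for the HIV endpoint and misplaced. The protocol does not say so, and an HIV-endpoint censoring rule is detail for the statistical analysis plan.

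**Conclusion.** The concern holds in limited form. Section 9.5 applies an HIV-test-based cut-off to behaviour. The last-negative-test limb discards valid reports without a stated reason, in a direction that cannot be determined. The infection limb censors the arms unequally and leaves unclear what the data kept under Sections 5.2.4 and 6.5.4 are for.

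The likely size is modest: a month-12 ratio of about 1.02 to 1.08 under no true difference, given an assumed deferred incidence of 5 per 100 person-years, the 44% to 73% reductions, and seroconverters reporting 2 to 3 times average risk. Apparent risk compensation is the direction only if those men stay above average; at average risk the ratio is 1.00, and below average it falls slightly under 1. At 250 per arm, sampling error is larger in every case computed. Severity is minor to moderate.

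**What to change.** Amend Section 9.5 in three ways:

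- **(a)** Remove censoring at the last negative HIV test for behaviour and STI outcomes, and use every report in the deferral period, as allocated.
- **(b)** State whether the target is behaviour while HIV negative or behaviour over all follow-up, and reconcile the choice with Sections 5.2.4 and 6.5.4.
- **(c)** If censoring at infection is kept for the main analysis, add a sensitivity analysis that includes post-infection questionnaires and STI screens.

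The cost is a revised sentence and one extra analysis, with no new data collection. The sensitivity analysis will be limited because seroconverters attend less, so it should report how many contributed data after infection in each arm. Making post-infection data the main analysis is a trade-off and is not required.
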